#### **9.3.4            *Cardiac Monitoring Device***

At 3 time points during the study, participants will wear a small device to collect continuous HR and rhythm data for approximately 48 hours ([Table 1](#)). The monitoring device uses surface electrodes, internal electronics to capture a continuous ECG waveform, removable memory card to store data over 48 hours, and a battery to power the device (see manual). Following a period of data collection, the memory card will be transported to a core laboratory where the continuous ECG waveforms will be uploaded for analysis. The analysis will provide full disclosure capabilities for HR and heart rhythm over the period during which the device was properly applied and functioning. The device will be used to explore the pattern of HR and heart rhythm before and during treatment with study drug.

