6. GENERAL STATISTICAL CONSIDERATIONS

The primary analysis will be conducted through the 30-week treatment period. Data collected through this time point will be cleaned and locked prior to conducting the primary analysis.

Once all participants have completed their Week 38/end of study (EOS) visit, all data will be cleaned and locked, and analyses using this data will be used to inform study objectives relating to follow-up safety and reversibility of drug effect.

SAS® version 9.4 or higher will be used for statistical analyses, tabulations, and graphical presentations.

In general, descriptive summaries will be presented by treatment group (placebo and mavacamten) for values at each visit. The descriptive summary for continuous variables will also be provided for the change from baseline and, if appropriate, for the change from week 30 to week 38. Summaries of continuous variables will include the number of subjects (N), mean, standard deviation (SD), median, Q1, Q3, minimum, and maximum. For variables with highly skewed distribution (e.g. log-normal distribution), geometric mean and %CV will also be reported in descriptive summaries. Inferential analysis for those variables may be performed after log-transformation as deemed appropriate. Descriptive summaries for categorical variables will include the number and percentage of subjects. Unless otherwise stated, denominators for percentages will be the number of subjects in the analysis population.

Between-group comparisons will focus on the comparative performance of mavacamten versus placebo. All statistical tests will be conducted at a 2-sided significance level of 0.05.

In general, baseline is defined as the last nonmissing value on or before the first dose date and time (as applicable). For certain data types (eg, accelerometer, PROs, cardiac rhythm monitoring, etc.), special considerations may be required. Refer to the specific data section for details.

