10.5. Cardiac Rhythm Monitoring (Including Holter Monitor)

The summary statistics of maximum HR, atrial fibrillation (Afib) percentage time, and VT (sustained or non-sustained) frequency will be calculated for each cumulative 48-hour Holter monitoring period and summarized by treatment group and visit. For each of the cardiac event type (Afib and VT), the number of subjects with ≥ 1 occurrence will be summarized. The percentage of time in Afib and number of VT episodes per subject will also be summarized. Additional parameters (eg, supraventricular tachycardia, premature ventricular contractions, pauses) may be summarized and analyzed as appropriate.

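### The default denominator for Holter VT occurrence counts unrecorded participants as VT-free, and the VT counts are not explicitly adjusted for analysable recording time

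*SAP*

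**What the plan says.** SAP 10.5 gives three VT summaries from the Holter:

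- VT frequency, which "will be calculated for each cumulative 48-hour Holter monitoring period and summarized by treatment group and visit".
- Occurrence: for Afib and for VT, "the number of subjects with ≥ 1 occurrence will be summarized".
- Episode count: the "number of VT episodes per subject will also be summarized".

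For atrial fibrillation the section also has a measure that carries its own time base: "The percentage of time in Afib". It sets no denominator for the occurrence summary, no divisor for analysable hours and no rule for short recordings.

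SAP 6 supplies the defaults. On format: "Descriptive summaries for categorical variables will include the number and percentage of subjects". On the denominator: "Unless otherwise stated, denominators for percentages will be the number of subjects in the analysis population". SAP 10 places all safety analyses on the Safety Analysis Population, which SAP 6.2 defines as randomized subjects who took at least one dose. A Holter recording is not required.

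Protocol 9.3.4 puts the recording length at about 48 hours and says the core laboratory's analysis holds "over the period during which the device was properly applied and functioning". Footnote l to Protocol Table 1 has the device applied at Screening, Week 12 and Week 26 only.

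**The concern.** A participant with no recording at Week 12 or Week 26 cannot enter the numerator for that visit but stays in the default denominator. In the table that person looks the same as someone monitored for 48 hours without VT. The percentage with at least one VT (and likewise with at least one Afib occurrence) is therefore too low whenever recordings are missing.

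Duration is a second, smaller matter. A recording with half the analysable time gives less opportunity to see VT, yet its episode count is pooled unadjusted with complete recordings.

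Ventricular tachyarrhythmia is a listed safety endpoint (Protocol 12.2.5), and the Holter is the scheduled continuous rhythm recording for all participants. If later recordings are less complete than those at Screening, the table could suggest a fall in VT within an arm that did not occur. If completeness differs between arms, it could show a difference that is not real or mask one that is.

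**Working it through.** The documents give no figure for Holter VT incidence, recording completeness or analysable hours, so there is nothing to reproduce. The rules can be followed through on the text. The sizes below are illustrations on assumed values.

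**Step 1: which denominator applies.** SAP 6 calls for a number and a percentage for categorical variables and uses the analysis population unless another denominator is stated. SAP 10.5 states none. The denominator is therefore every dosed participant in the arm.

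**Step 2: does the missing-data rule change this?** SAP 6.4 says missing data are generally not imputed. That keeps an invented value out of the numerator. It does not take the person out of the denominator, so the effect on the percentage is the same as recording no VT.

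**Step 3: can recordings be absent?** Yes. The device is applied at three time points, and Protocol 10.1.4 allows a participant to stop follow-up after the early termination visit. In addition, SAP 6 tabulates safety data by nominal visit and relabels visits after early termination as FU-1, FU-2 and so on. Read literally, a Week 26 recording made after early termination leaves the Week 26 row while the participant stays in its denominator.

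**Step 4: size of the denominator effect.** With true proportion p and missing share m, and missingness unrelated to VT:

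reported = (1 − m) × p

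| True p | 5% missing | 10% missing | 20% missing |
|---|---|---|---|
| 10% | 9.5% | 9.0% | 8.0% |
| 20% | 19.0% | 18.0% | 16.0% |
| 30% | 28.5% | 27.0% | 24.0% |

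For example, 0.90 × 0.20 = 0.18. With 110 per arm, the planned size, that is 19.8 participants shown instead of 22.

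**Step 5: effect of short recordings.** Assume a constant VT rate (Poisson) that gives proportion p over 48 hours. Over T analysable hours:

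P(at least one VT) = 1 − (1 − p)^(T/48)

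For p = 20%, 36 hours gives 1 − 0.80^0.75 = 15.4%, and 24 hours gives 1 − 0.80^0.50 = 10.6%. For p = 10% the values are 7.6% and 5.1%; for p = 30%, 23.5% and 16.3%. The expected episode count scales as T/48: 0.75 of the 48-hour value at 36 hours and 0.50 at 24 hours. With 36-hour recordings and 10% missing together, a true 20% shows as 0.90 × 15.4% = 13.9%.

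**Step 6: between arms.** With equal true VT of 20% and 5% against 15% missing, the table shows 0.95 × 20% = 19.0% against 0.85 × 20% = 17.0%. That is a false difference of 2.0 points (ratio 0.89), favouring whichever arm has more missing. With equal missingness and duration, equal true rates give equal reported rates.

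**The case against.** The strongest reply is that SAP 10.5 names only a number of subjects, not a percentage, and that VT frequency is already given per 48-hour period. Continuous summaries report N (SAP 6), so the N behind maximum heart rate, Afib time and VT frequency should let a reader see how many were recorded by arm and visit and recompute the percentage.

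Part of this stands. VT is not wholly without a time frame, and the raw count of subjects with VT is not wrong in itself. But SAP 6 adds a percentage to categorical summaries and fixes its denominator, so the fault comes from a stated rule. The 48-hour period is nominal: it may be read as a rate per 48 recorded hours, but no rule adjusts a shorter recording. A reader's ability to repair the percentage is not a reason to publish the unrepaired one.

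Several stronger inferences are tempting and are not supported:

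- *Unrecorded participants add zeros to episodes per subject.* With no imputation they need not. The denominator fault concerns the occurrence percentage.
- *Temporary holds cause missing recordings.* Protocol 7.3.2 does not end scheduled visits during a hold, and Protocol 10.1.4 asks that participants keep attending even after permanent discontinuation.
- *A mavacamten excess would be hidden.* Nothing in the documents shows that completeness differs by arm, or in which direction.
- *The ventricular tachyarrhythmia endpoint itself is understated.* Protocol 9.3 has these events adjudicated, and adverse event reports and ICD downloads also contribute. Protocol 9.3.4 describes the device as a means of exploring rate and rhythm patterns.

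**Conclusion.** The point holds in limited form. Under the stated defaults, the percentage of participants with at least one VT on Holter at a visit is understated by the factor (1 − m), where m is the share of dosed participants without a recording tabulated at that visit. Episodes per subject, and frequency per nominal 48 hours, lack an explicit adjustment for analysable time.

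The direction within an arm follows from arithmetic; the size does not follow from the documents. Every prevalence, missing share and recording length used above is an assumption, and the duration figures also assume a constant rate with independent episodes, so clustered VT would behave differently. Any bias between arms depends on unequal completeness or duration, and its direction is unknown.

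The consequence is modest. SAP 10 makes safety analysis descriptive with no hypothesis test, and the primary analysis is not touched. The change is worth making because it costs little and improves on the stated rule.

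**What to change.** In SAP 10.5:

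1. For the percentage with at least one VT (or Afib) occurrence, use as denominator the participants with an analysable recording at that visit.
2. Report VT episodes per 24 (or 48) analysable hours alongside the raw count per subject.
3. Show the number recorded and the median analysable hours by arm and visit.
4. State at which visit a recording made after early termination is tabulated.

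Keep short recordings in the occurrence table. A minimum-duration rule there would remove VT that was actually observed, and a 24-hour minimum would still admit recordings that show 10.6% in place of 20% in the illustration. At most, add a sensitivity summary limited to near-complete recordings. The occurrence percentage will still depend on duration, which is why items 2 and 3 belong beside it. The new denominator restores the true percentage only if missingness is unrelated to VT and recordings are complete.

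The cost is SAP wording, one derived variable and slightly smaller denominators, provided the core laboratory supplies analysable time. No new data collection is needed.

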10.6. Other Safety Analysis

Listing of patients with ICD therapy (shock) and appropriateness of therapy as per event adjudication will be provided.

Abnormal physical examination results will be listed by subject and clinical significance.

The number of subjects who met treatment discontinuation criteria per protocol, as well as who met each temporary study drug interruption, will be summarized by treatment and criteria met.

[REDACTED]

[figure not shown]
13. INTERIM ANALYSIS

No interim analysis is planned for this study. Week 30 analysis is the primary analysis to evaluate the efficacy, and week 38 analysis is the safety follow up analysis.

14. SUMMARY OF CHANGES IN THE PROTOCOL PLANNED ANALYSES

APPENDIX 1.

Figure 1: Study Schema

Abbreviations: CPET, cardiopulmonary exercise testing; ECG, electrocardiogram; PK, pharmacokinetics; QD, once daily; stress echo, post-exercise stress echocardiography; TTE, transthoracic echocardiogram; wks, weeks.

Table 4: Schedule of Study Procedures

Table 4: Schedule of Study Procedures (Continued)

Assessment ^a	Screening ^b Day -35 to Day -1	Day 1	Week 4 (±7 d)	Week 6 (±7 d)	Week 8 (±7 d)	Week 12 (±7 d)	Week 14 (±7 d)	Week 18 (±7 d)	Week 22 (±7 d)	Week 26 (±7 d)	ET ^c	Week 30 (±7 d)/ EOT	Week 34 (±7 d) (call)	Week 38 (±7 d)/ EOS
FSH ^p	X													
Serum pregnancy test (women) ^q	X													
Urine pregnancy test (women) ^q		X	X		X	X		X	X	X	X	X	X	X
██████████		X												
██████████	X													
██████████		X									X	X		
Symptom Assessment														
NYHA functional classification	X	X	X	X	X	X	X	X	X	X	X	X		X
Patient-Reported Outcomes														
Investigational Medical Product														
IMP QD		←									→			
IMP administered at site ^t		X	X	X	X	X	X	X	X	X		X		
IMP compliance ^u			X	X	X	X	X	X	X	X	X	X	X	
Substudy														
██████████		X										X		

Abbreviations: AE, adverse event; BP, blood pressure; call, telephone contact; CMR, cardiac magnetic resonance imaging; CPET, cardiopulmonary exercise testing; CYP, cytochrome P450; d, day; DNA, deoxyribonucleic acid; ECG, electrocardiogram; EOS, end of study; EOT, end of treatment; ET, early termination; FSH, follicle-stimulating hormone; HCM, hypertrophic cardiomyopathy; HIV, human immunodeficiency virus; HR, heart rate; hs, high-sensitivity; ICD, implantable cardioverter-defibrillator; ICF, informed consent form; IMP, investigational medicinal product; LVOT, left ventricular outflow tract; NT-proBNP, N-terminal pro b-type natriuretic peptide; NYHA, New York Heart Association; PK, pharmacokinetic; PRO, patient-reported outcomes; QD, once daily; QTcF, Fridericia correction; SAE, serious adverse event; TTE, transthoracic echocardiography.

^a Preferred order of assessments is ECG, vital signs, PK, and TTE, all prior to study drug dosing unless otherwise described below.

^b Screening will require more than 1 visit to accommodate all of the study procedures.

^c The ET visit will be scheduled as soon as possible after the participant permanently discontinues study drug. The participant will be encouraged to participate in the remaining scheduled study visits, particularly the Week 30 visit and the Week 38/EOS visit. If a participant permanently discontinues treatment at or before Week 22, the final visit will be at Week 30.

^d At Screening, ET, Week 30/EOT, and Week 38, a complete physical examination will be conducted, including a neurological examination. At all other visits, an abbreviated cardiopulmonary physical examination will be conducted, with other systems assessed as directed by interval history.

Table 4: Schedule of Study Procedures (Continued)

- ^e Changes in baseline conditions from once the ICF is signed will be recorded as an AE. All changes unless otherwise specified that occur after the administration of study drug will be considered treatment-emergent AEs. This assessment will occur either by phone call or an in-person visit.
- ^f For participants who have ICDs, information including rhythm strips and events will be downloaded from the ICDs at baseline, at Week 12, and at Week 30, or as clinically indicated after any ICD discharge interrogation occurring during the double-blind treatment period.
- ^g Twelve (12)-lead ECGs will be performed after 10 minutes of rest at Screening and prior to dosing at all onsite study visits (except Weeks 8 and 14). Each time an ECG is completed, a 10-second paper ECG will be obtained and maintained in the study participant's source documentation. QTcF value from Day 1 ECG will not be used for eligibility or for temporary discontinuation. The Day 1 QTcF value will be used as the baseline to determine percent change at future visits when criteria for temporary discontinuation are applied. (Note: If for any reason a D1 QTcF is not determined, then QTcF from screening ECG will be used in percent change calculation.)
- ^h At Screening, ET, Week 30/EOT, and Week 38, complete vital signs including temperature, HR, respiratory rate, and BP will be obtained. At all other visits, only HR and BP are required. If PK sampling is conducted at a visit, vital signs should be collected before PK sampling. Vital signs should be taken with the study participant in the same position at all visits. BP should be taken via an automated recorder after resting for at least 5 minutes.
- ⁱ Resting TTE should be performed prior to post-exercise stress echocardiography or CPET. Resting TTE images and views will be acquired at each onsite visit prior to dosing as detailed in the echo site instruction manual. Instantaneous LVOT peak gradient (resting) and provoked LVOT peak gradient (Valsalva maneuver) will be assessed by the core laboratory. Left ventricular ejection fraction (LVEF) will be measured at the clinical site by the certified site sonographer and subsequently by the core laboratory. The LVEF site read will be kept blinded from the investigator and other study site personnel, except in case of locally measured LVEF \leq 30%.
- ^j For post-exercise stress echocardiography, participants will undergo a standard symptom-limited exercise test after a 4-hour fast by standardized treadmill or bicycle ergometer during Screening and Week 30/EOT prior to dosing. Instantaneous LVOT peak gradient will be assessed immediately post-exercise by TTE. Post-exercise stress echocardiography may be performed on a different day than CPET. If the 2 procedures are performed on the same day, participants must exercise only once, and participants will undergo CPET and then post-exercise TTE. Post-exercise stress echocardiography should be acquired the same day or within 72 hours of the Resting TTE and should also be performed as close as possible to ET if it occurs. If post-exercise stress echocardiography and CPET are performed on different days, the same sequence of visits must be performed for both screening and EOT.
- ^k CPET by standardized treadmill or bicycle ergometer will be performed during Screening and at Week 30/EOT prior to dosing. CPET is done after a 4-hour fast. Record the fasting status and the date and time of the last dose taken prior to CPET. Any concomitant medication may be administered prior to all exercise testing. CPET should also be performed as close as possible to ET if it occurs.
- ^l A cardiac monitoring device will be applied during Screening, Week 12, and at the Week 26 visits and retrieved at the Day 1, Week 14, and Week 30 visits, respectively.
- ^m An accelerometer will be fastened to the participant's wrist at Screening (at least 11 days before Day 1) and at the Week 26 visit to collect data on activity. Participants will return the accelerometer at the next study visit for data upload and analysis.
- ⁿ Participants should not take study drug on day of visit prior to blood draw for PK. PK sample will be collected \leq 2 hours before dosing. Additionally, on Week 30 (last dose), another PK sample will be collected within 1 to 2 hours postdose.
- ^o NT-proBNP should be drawn before exercise testing if exercise testing is being performed that day.
- ^p FSH testing at Screening for postmenopausal women to confirm postmenopausal status.
- ^q Pregnancy testing for all females of childbearing potential: serum pregnancy test at Screening; urine pregnancy test at all other visits shown (every 4-6 weeks), and conduct serum test if any urine test is positive. The Week 34 pregnancy testing will be conducted at home.

Table 4: Schedule of Study Procedures (Continued)

- ^r Separate consent is required for HCM genotyping. Note that if a participant with a prior HCM clinical genotype test that was positive for genetic mutation consents to provide their results, then no further genotype assessment will be performed; however, participants who have not been tested, participants who have tested negative for HCM mutations on clinical panels, and participants who have a positive HCM genotype result but cannot provide the results or will not consent to provide the results may consent to have blood drawn on Day 1 for assessment of HCM genotype.
- ^s The pharmacogenetic panel will include CYP 2C19 genotyping and potentially additional DNA sequencing. Pharmacogenetic Screening for CYP 2C19 genotyping will occur at Screening; samples from screen failures must be destroyed.
- ^t At all onsite visits, study drug will be administered at the investigational site to facilitate collection of PK samples \leq 2 hours prior to dosing. Note: There is no PK sample at Day 1 or Week 14. With the exception of Week 30 when a PK sample is also drawn within 1 to 2 hours postdose, Study drug will be administered at the end of the visit when all other assessments have been done, including any drawing of blood.
- ^u All participants will return their study drug dosing containers to the site pharmacy for capsule counts. Refer to the Pharmacy Manual for details.
- ^v The CMR substudy assessment can be completed up to 5 days before the Day 1 visit and up to 5 days before the EOT visit.

APPENDIX 2.

Table 5: Analysis Window Definition for NYHA class and NT-proBNP

Analysis Visit	Analysis Visit Window	Analysis Visit Target Day
Baseline	Screening <= analysis day <=1	1
Week 4	15 < analysis day <= 36	29
Week 6	36 < analysis day <= 50	43
Week 8	50 < analysis day <= 71	57
Week 12	71 < analysis day <= 92	85
Week 14	92 < analysis day <=113	99
Week 18	113< analysis day <=141	127
Week 22	141< analysis day <=169	155
Week 26	169<analysis day <=197	183
Week 30	197<analysis day <=239	211
Week 38	239<analysis day <=295	267

Table 6: Analysis Window Definition for CPET, Stress Echo and CMR Measurements

Analysis Visit	Analysis Visit Window	Analysis Visit Target Day
Baseline	Screening <= analysis day <=1	1
Week 30	183 < analysis day <= 239	211

Table 7: Analysis Window Definition for Resting TTE

Analysis Visit	Analysis Visit Window	Analysis Visit Target Day
Baseline	Screening <= analysis day <=1	1
Week 4	15 < analysis day <= 36	29
Week 6	36 < analysis day <= 57	43
Week 12	71 < analysis day <= 99	85
Week 18	113< analysis day <=141	127
Week 22	141< analysis day <=169	155
Week 26	169<analysis day <=197	183
Week 30	197<analysis day <=239	211
Week 38	239<analysis day <=295	267

Table 8: Analysis Window Definition for hs-Cardiac Troponin I

Analysis Visit	Analysis Visit Window	Analysis Visit Target Day
Baseline	Screening <= analysis day <=1	1
Week 6	29 < analysis day <=57	43
Week 18	113<analysis day <=141	127
Week 30	197 < analysis day<=239	211
Week 38	239<analysis day<=295	267

Table 9: Analysis Window Definition for PGIS and PGIC

Analysis Visit	Analysis Visit Window	Analysis Visit Target Day
Baseline	Screening <= analysis day <=1	1
Week 6	29 < analysis day <= 57	43
Week 10	57 < analysis day <= 85	71
Week 14	85 < analysis day <=113	99
Week 18	113<analysis day <=141	127
Week 22	141< analysis day <=169	155
Week 26	169<analysis day <=197	183
Week 30	197<analysis day <=239	211
Week 38	239<analysis day <=295	267

Table 10: Analysis Window Definition for WPAI-SHP, EQ-5D-5L, and KCCQ-23

Analysis Visit	Analysis Visit Window	Analysis Visit Target Day
Baseline	Screening <= analysis day <=1	1
Week 6	29 < analysis day <= 57	43
Week 12	71 < analysis day <= 99	85
Week 18	113< analysis day <=155	127
Week 30	197<analysis day <=239	211
Week 38	239<analysis day <=295	267

Table 11: Analysis Window Definition for HCMSQ

Analysis Visit	Analysis Visit Window	Analysis Visit Target Day
Baseline	Screening <= analysis day <= 1	1
Week 4	15 <= analysis day < 36	29
Week 6	36 <= analysis day < 57	43
Week 10	57 <= analysis day < 85	71
Week 14	85 <= analysis day < 113	99
Week 18	113 <= analysis day < 141	127
Week 22	141 <= analysis day < 169	155
Week 26	169 <= analysis day < 197	183
Week 30	197 <= analysis day < 239	211
Week 38	239 <= analysis day < 295	267

Signature Page for VV-CLIN-000034

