5. DETERMINATION OF SAMPLE SIZE

Approximately 220 participants will be randomized, with 110 participants in each of the 2 groups. Randomization will be stratified for NYHA class (II or III), current treatment with β -blocker (yes/no), type of ergometer (treadmill or exercise bicycle), and consent for the CMR substudy (yes or no). The sample size should provide adequate power to determine the superiority of mavacamten in improving peak oxygen consumption (pVO₂) and NYHA class relative to placebo (see Section 12.2.1 of the protocol). The power calculation is derived

assuming a true clinically meaningful difference of 25% between mavacamten and placebo participants in achieving the clinical response. Based on the MYK-461-004 PIONEER-HCM Phase 2 study, 50% of the participants receiving mavacamten met the clinical responder definition by the end of 12-week treatment period. Assuming the same percentage of participants in the active treatment arm and 25% in placebo arm will achieve the clinical response at the end of the 30-week dosing period in the current study, the proposed sample size of 110 participants per arm will provide 96% power at the 2-sided 5% statistical significance level. Participants who terminate early or cannot be assessed for the clinical response at the end of the 30-week dosing period will be considered nonresponders.

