Unless otherwise noted, nonsafety (ie. efficacy, pharmacodynamics [PD]) information displayed “by visit” will utilize analysis visits as defined by the analysis visit window as opposed to the visits at which the information was collected (ie, nominal visit). Data collected at unscheduled or early termination (ET) visits will also be mapped to analysis visits. The analysis day for the purposes of deriving the analysis visit windows are derived as follows (reference date is the study drug initiation date, or the randomization date if the study drug initiation date is missing):

- If date of information (year, month, and day) is completely missing, analysis day cannot be calculated and will be treated as missing. If the date is partially missing, date will be imputed according to the rules outlined in [Section 6.4](#).
- If date is < reference date, analysis day = date of information – reference date. If date \geq reference date, analysis day = (date of information – reference date) + 1.

The visit windows for efficacy and PD assessments will be defined according to their respective collection schedules. The rule for defining the analysis window is +/-14 days from the target visit date for all post-baseline visits, except for Week 30 and Week 38, which have +/- 28 day windows. If 2 adjacent visit windows overlap, the limits of the windows will be adjusted to the midpoint between the 2 visits. The specific window definitions for each endpoint are available in Appendix 2 [Table 3 to Table 9](#).

For efficacy and PD analyses, if a value does not fall within an analysis window, it will not be included in the summary analysis. However, these values will be included in data listings and SAS data sets. For post-baseline data, when more than 1 value is available within the same analysis visit, the value collected closest to the target visit day will be used for analysis. If 2 values are the same distance to the closest to target visit day (for example, 1 value is before and the other value is after the target day), then the latest value will be selected as the analysis value. For a specific analysis window, if the latest collected time point has 2 or more values collected, then for continuous data, the average among these results will be derived, and for categorical data (eg, yes or no) the clinically ‘worse’ value will be selected.

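### Do the different Week 30 windows for CPET and NYHA class, with early-termination data mapped into them, leave the primary endpoint open to conflicting scoring?

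*SAP*

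**What the plan says.** Clinical response (SAP Section 6.1) joins a change in pVO2 with a change in NYHA class at Week 30. SAP Appendix 2 sets windows measure by measure:

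- **CPET (Table 6).** Week 30 is "183 < analysis day <= 239", that is, days 184 to 239.
- **NYHA class (Table 5).** Week 30 is "197<analysis day <=239", days 198 to 239. The row above it, Week 26, is "169<analysis day <=197", days 170 to 197.

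SAP Section 6 gives the rules behind these limits. Windows are 14 days either side of target, "except for Week 30 and Week 38, which have +/- 28 day windows". Then: "If 2 adjacent visit windows overlap, the limits of the windows will be adjusted to the midpoint between the 2 visits". On early termination it says: "Data collected at unscheduled or early termination (ET) visits will also be mapped to analysis visits". Where a window holds several values, "the value collected closest to the target visit day will be used for analysis".

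SAP Section 5 sets the rule for the responder endpoint: "Participants who terminate early or cannot be assessed for the clinical response at the end of the 30-week dosing period will be considered nonresponders". The protocol has the same rule in its Synopsis and in Sections 12.1 and 12.4.6.1. SAP Section 6.4 refers the reader to Sections 8.1 and 8.2 for handling in the responder analyses. Neither section appears in the public version.

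**The concern.** The ET visit collects both CPET and NYHA class. If it falls on days 184 to 197, the pVO2 is labelled Week 30 and the NYHA class from the same day is labelled Week 26. The participant then seems unassessable although both components were measured together.

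Participants who stop treatment are also encouraged to attend Week 30. If one attends without repeating CPET, an ET pVO2 taken soon after stopping could be joined to an NYHA class recorded weeks later. Meanwhile Section 5 appears to make the same person a nonresponder outright.

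At stake is the classification of individuals on a binary primary endpoint. Some reasons for stopping permanently (LVEF at or below 30%, heart failure with systolic dysfunction) relate to the drug's expected risk, so affected cases need not be balanced between arms.

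**Working it through.** **1. Reproduce the windows.** Target day = 7 × week + 1, which gives 183 (Week 26), 211 (Week 30) and 267 (Week 38).

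- Week 30: 211 ± 28 = 183 to 239.
- Week 26: 183 ± 14 = 169 to 197.
- Week 38: 267 − 28 = 239, so it meets Week 30 without overlap.
- NYHA class is recorded at Week 26, so the two windows overlap and are cut at (183 + 211)/2 = 197.
- CPET has no Week 26 assessment, so nothing is cut.

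Both tables are reproduced exactly. The CPET window has 239 − 183 = 56 days and the NYHA window has 239 − 197 = 42. The difference is 14 days, 184 to 197.

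**2. Follow an ET visit through the rules.**

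| Day of ET visit | pVO2 maps to | NYHA maps to | Result |
|---|---|---|---|
| 183 or earlier | no window | Week 26 or earlier | Nonresponder |
| 184–197, no later visit | Week 30 | Week 26 | Nonresponder as an early terminator, and also as unassessable |
| 184–197, later NYHA on 198–239, no later CPET | Week 30 | Week 30, later date | Nonresponder by Section 5; scored on mixed dates only if that rule is set aside |
| 198 up to the Week 30 visit | Week 30 | Week 30 | Nonresponder by Section 5; scored on values only if mapping overrides it |

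There are two possible results: nonresponder, or scored on values. In the gap itself, with no later visit, the rules agree.

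**3. What mis-pairing requires.** For an ET visit in the gap, four things must coincide: the ET visit on days 184–197, an NYHA class on days 198–239, no CPET at that later visit, and the nonresponder rule not applied. The largest separation would be 239 − 184 = 55 days. Protocol Section 10.1.4 puts particular weight on a final CPET at Week 30 for those who stop. If it is done on schedule, the closest-to-target rule selects it over the ET value.

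**4. How many.** The documents give no early-termination rate. Assume that 5%, 10% or 15% of 220 stop, uniformly over 210 days.

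- Days 184–197: 220 × rate × 14/210 = 0.7, 1.5 or 2.2.
- Adding days 198–203, before the Week 30 visit window (211 ± 7 = 204 to 218): 220 × rate × 20/210 = 1.0, 2.1 or 3.1.

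These are upper figures for the problem, because most of these participants are nonresponders on either reading.

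**5. Power as a yardstick.** With 110 per arm and 50% versus 25%:

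- Pooled: (0.25 − 1.96 × √(2 × 0.375 × 0.625/110)) / √((0.25 + 0.1875)/110) = (0.25 − 0.1279)/0.0631 = 1.935, or 97.4%.
- Continuity-corrected: (0.25 − 1/110 − 0.1279)/0.0631 = 1.79, or 96.3%, which matches the stated 96%.

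Suppose 1%, 2% or 5% of would-be responders in both arms became nonresponders. Pooled power would be 97.2%, 96.9% or 96.2%. If only the active arm were affected, it would be 96.9%, 96.3% or 94.0%.

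**6. What a tighter rule would do.** Starting the CPET window at day 198, or requiring the two components within 7 days, would leave early terminators as nonresponders, which Section 5 already makes them. It would also reach participants still on treatment. A CPET on day 195 with NYHA class on day 211 (16 days apart) is scored now and would become a nonresponse. The protocol lets the post-exercise echocardiogram fall between Weeks 26 and 30, and allows one exercise session to serve both tests, so an early CPET is plausible.

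**The case for a change.** The strongest case for a change is that a midpoint rule applied measure by measure does not suit an endpoint that joins two measures, and that no visible text requires both to come from one visit. Closest-to-target selection is also made separately for each measure. An ET visit with both components on day 200, followed by a Week 30 visit with NYHA class only, would be mis-paired even with identical windows. The difference in exposure would be real: the protocol equates 56 days with five half-lives, about 11.2 days each, so 21 days after stopping the drug level is about 0.5^(21/11.2) = 27%. The windows also reach the secondary endpoints, where a day-190 ET visit supplies Week 30 pVO2 but not Week 30 NYHA class.

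Part of this stands. The visible text does not say whether terminating early means stopping treatment or leaving the study. The SAP's wording could mean either, and the protocol's statistical section speaks of dropouts. That question concerns anyone who stops treatment and returns at Week 30, not only those in the 14-day gap. No visible sentence ranks the nonresponder rule above the mapping rule.

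It does not carry the conclusion. The mapping sentence is a general rule for displays by visit and yields where the SAP says otherwise. The nonresponder rule is specific to clinical response and is repeated consistently. On an ordinary reading, mapping places a value in a visit and the specific rule sets responder status. Sections 8.1 and 8.2 are where the remaining detail belongs, and their absence from the public text does not show that the plan lacks it. For the secondaries, each endpoint uses the window that fits its own collection schedule, which is stated policy.

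**Conclusion.** No change is called for. The window limits differ because the SAP's overlap rule was applied correctly to two measures with different schedules. Where the mismatch occurs, an ET visit without a later visit gives the same answer under every visible rule. Where the answers could differ (an ET visit from day 198, or a later NYHA class with no repeat CPET), the specific nonresponder rule settles the matter on an ordinary reading.

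The number involved is about 2 or fewer of 220 in the gap, and about 3 or fewer with days 198–203 added, at assumed stopping rates up to 15% with uniform timing. Fewer still could be mis-scored. What remains is a point of detail, the meaning of early termination and its precedence over mapping, which the withheld Sections 8.1 and 8.2 may already cover. A shared window or a 7-day match has no demonstrated gain and could cost a participant on treatment a valid assessment. The conclusion rests on the nonresponder rule being applied as written. It would need another look if Section 8.1 let ET values supply the composite.
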